Protocol Title: Text BP: Comparing standard office based follow up versus text-based remote monitoring in the management of postpartum hypertension.

NCT number: 03185455

Date of Document: 11/9/2016

Protocol title: TextBP: Comparing standard office based follow up versus text-based remote monitoring in the management of postpartum hypertension

Short title: Remote surveillance of postpartum hypertension

Brief description of protocol:

Women with hypertensive disorders of pregnancy need postpartum blood pressure (BP) surveillance to detect persistent hypertension. Various barriers result in only 30% attendance at postpartum BP visits. A more effective strategy is needed. Women with hypertension of pregnancy will be randomized to either text-based monitoring or office visits. Those randomized to the intervention will receive a BP cuff and text in their BP to an automated, clinician derived, HIPAA compliant text-based algorithm.

Abstract:

Hypertension is a leading cause of maternal morbidity, mortality and obstetrical readmissions. Peak blood pressure usually occurs 3-6 days postpartum, and is typically unaccompanied by warning symptoms. Although there is a clear need for effective and reliable blood pressure surveillance after delivery, there are significant obstacles to in-person visits in the immediate postpartum period, including sleep deprivation, newborn care, and transportation needs. These barriers have proven real as we observed only 30-50% attendance to office blood pressure visits following delivery. This proposal will investigate whether text-based communication between patients and providers is an effective alternative method for monitoring postpartum hypertension in at risk women.

Women with hypertensive disorders of pregnancy with access to a cell phone with unlimited text message capabilities will be randomized to either office visit blood pressure checks after discharge or receive a blood pressure cuff and text in blood pressures for two weeks postpartum using a standardized, HIPAA compliant, physician derived automated platform.

Objectives

Overall objectives:

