The objective of this study is to compare office based blood pressure visits (standard of care) to remote surveillance using a text-messaging system for monitoring postpartum hypertension. The goal of this study is to determine if text messaging is an effective, patient centered way to monitor blood pressure in the postpartum period. By supporting patient self-care and using health information technology, we hope to adopt a method that can achieve best outcomes in our current patient, largely underserved minority population.

Primary outcome variables:

The primary outcome is the percentage of patients in which a single blood pressure is obtained in the first 10 days following discharge. Within the texting group, the percentage of patients in whom blood pressure values are obtained at 72 hours and 7-10 days postpartum, in accordance with ACOG recommendations, will be assessed as well.

Secondary outcome variables:

Secondary outcomes will include ability of providers to initiate antihypertensive medication, number of postpartum emergency room visits for hypertension and readmissions for persistent postpartum hypertension, patient satisfaction with blood pressure surveillance, and future health awareness/patient engagement by assessing number of patients with a primary care/cardiology appointment scheduled by two weeks postpartum. Additionally, cost data will be compared between the two arms.

Background:

Hypertensive disease is a leading cause of maternal morbidity and mortality and obstetrical readmissions in the US, accounting for 27% of the obstetric readmissions in 2009. The majority of patients readmitted with hypertension are diagnosed with a hypertensive disorder of pregnancy on initial admission for delivery, indicating that these readmissions result from disease progression in contrast to new onset disease, and are plausibly preventable. Given the risk of strokes and seizures from persistent or worsening disease, early recognition of progression and aggressive treatment is critical in the postpartum period. For these reasons, identifying patients who are at risk for persistent disease and being proactive in their postpartum care can decrease maternal morbidity.

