Given the significant morbidity and mortality attributable to preeclampsia and persistent and progressive postpartum disease coupled with 1) the observation that postpartum hypertension is the leading cause of obstetrical readmissions (over 45% of all readmissions within 7 days in Fiscal Year 14) and 2) our current surveillance is inadequate and generally reaches fewer than half of all women at risk, we sought to test an innovative approach to surveillance using sms-text messaging as an alternative to in-person follow up.

With support and partnership through the Penn Medicine Center for Health Care Innovation, we previously performed a small pilot study of 32 women with hypertensive disorders of pregnancy. The goal of this initial pilot was to determine if we could engage patients in remote postpartum hypertension surveillance and obtain important and necessary preparatory patient feedback to develop this proposal. Patients were provided with a home blood pressure cuff and were instructed on its use.

They were asked to send in blood pressures on the seven days following discharge from the hospital after their delivery. We found that 84% of the patients engaged in the study and texted at least one blood pressure in the 7 days and nearly 65% of patients sent in blood pressures on 5 of the 7 days requested. Of the 32 patients in the pilot, only six (19%) returned for their scheduled office blood pressure check (routine care). Patients reported that text messaging was an active way for them to participate in their care and increased their awareness of postpartum hypertension.

While we found remote surveillance of blood pressure with mobile phone texting to be a feasible, convenient, affordable, and patient-centered way for patients and providers to monitor blood pressure in the postpartum period, further testing is needed prior to widespread adoption. We have since developed a bidirectional, HIPAA compliant, clinician derived, automated text based hypertension algorithm that provides reminders to patients to text in blood pressures, timely automated responses to patient texts based on a preset clinical blood pressure algorithm, and alerts clinicians to preset high blood pressure values that require response. We have already tested this with seven patients and received feedback ensuring its functionality.

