Using this two-way text based clinician derived automated hypertension algorithm, we will perform a randomized controlled trial comparing the effectiveness of these two strategies usual visit based care to this text based innovative strategy. Our overall goal is to improve postpartum blood pressure monitoring in women with a previously diagnosed hypertensive disorder of pregnancy. If, in fact, text message surveillance decreases maternal morbidity and readmissions, this would have large implications for patient care and enhance the way we perform postpartum blood pressure monitoring. Additionally, this has potential generalizability to other populations that require frequent blood pressure monitoring (adult cardiovascular, heart failure, etc.) as well as possible use in monitoring other postpartum conditions (depression, breastfeeding).

Study design

Design:

The study will be an un-blinded randomized, two arm trial. Patient will be randomized to usual one time office visit based blood pressure check or to text-message based remote surveillance for two weeks. Randomization will be performed using a computer generated sequence using REDCAP. Demographic information will be collected from those who decline randomization or are ineligible in order to assess patient characteristics of those willing to be randomized and who meet eligibility.

Study duration:

Estimated length of time is 12 months. We believe it will take no more than 9 months to enroll all of the patients and allow three months for data analysis. This is based on our previous ability to enroll patients in a pilot study investigating remote surveillance. The subjects will participate in the study for two weeks (14 days) following discharge if they are randomized to the text-message arm.

Resources necessary for human research protections:

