Our sample size calculation is based on the show rate for office blood pressure visits since initiation of this standard of care and the results from our pilot study. The range of show rates in these office visits is 30-50% and our preliminary data suggests that approximately 80% of patients text at least one blood pressure in the 7 days post discharge. Using a more conservative usual care show rate of 50%, with an alpha of 0.05, 80% power and using a 2-sided t-test, we would require 103 patients in each arm to detect this 1.4 fold increase blood pressure ascertainment.

Key inclusion criteria:

Women with chronic hypertension, gestational hypertension, or preeclampsia who deliver at HUP will be eligible. All patients must be 18 years old, able to speak and read English, have a hypertension diagnosis listed above, and have access to a cell phone with unlimited text message capabilities.

Key exclusion criteria:

Women without access to a cell phone with unlimited text message capabilities will be excluded from the study in order to eliminate barriers to participate in remote surveillance. However, we will track the number of women not eligible for this reason in order to understand generalizability in an urban population. Women who cannot read or speak English or are younger than 18 years of age will be ineligible.

Populations vulnerable to undue influence or coercion:

Patients will specifically be told what arm they are in following randomization. Those not randomized to text-messaging and those electing not to participate will receive the current standard of care (office based visit).

Subject recruitment:

Eligibility will be determined in the postpartum period on the postpartum recovery unit by the research team which will include the Maternal Fetal Medicine fellows, the MCHRP inpatient clinical research coordinator team, and postpartum nursing leadership (see eligibility algorithm). Women will be approached at time of their routine hypertension education, prior to discharge, by the research coordinators. Enrollment in the study will take place at this time if they agree, and entry into the automated platform will occur prior to discharge for those randomized to this arm. Those randomized to usual care will receive their office visit date/time prior to discharge.

Subject compensation:

None

Procedures:

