The study will be performed as a pilot randomized control trial. Patients will be randomized to either having routine office based blood pressure check visit or to remote text-message based surveillance using a previously developed automated algorithm (WaytoHealth). Study flow chart is attached.

Postpartum patients with a hypertensive disorder of pregnancy will be approached for enrollment by trained study personnel on the recovery unit. Participants will be randomized 1:1 using a computer generated random number table of permuted blocks. Recruitment will occur prior to discharge at time of hypertension education and randomization will occur once consent is obtained.

Those randomized to the standard protocol for blood pressure monitoring will be scheduled for an office based nursing blood pressure visits 4-6 days postpartum. The date and time of the office appointment is specified in the discharge document and reviewed with the patient prior to discharge. Care at this visit is based on a physician derived algorithm. Women randomized to the text-based surveillance arm will be given an automatic Omron® blood pressure cuff and instructed on its use by research team members prior to discharge. Patients will be enrolled into the texting program platform developed through Way to Health. A starting introductory text message is sent by the Way to Health platform to the phone number provided on day of discharge. Patients receive reminders to text message their blood pressures twice daily for two weeks postpartum, starting on the day after discharge. Immediate feedback is provided to the patient based on a preprogrammed automated algorithm. The primary investigator is alerted with pre-specified severe range blood pressure values (systolic blood pressure > 160 mmHg or diastolic > 100 mmHg) via text message or email and care is escalated as needed based on the same outpatient algorithm used in the office. All patients will receive a phone call 3 weeks after delivery for a patient satisfaction survey. All patients will be instructed to return for their usual postpartum visit at 4-6 weeks.

Analysis plan:

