Consent will be obtained by the study investigators or assigned research staff when receiving postpartum hypertension education prior to discharge. The study will be explained in lay person terms to each eligible woman by one of the investigators or assigned research staff. The consent form will be given to the patient and she will have ample time to read the consent form on her own. The woman will be asked if she has any questions regarding the study protocol or the consent form. All questions will be answered. The woman will be informed that her care will not be affected if she chooses not to participate in the study and that she may discontinue participation at any time point. She will be made aware of what is needed in the intervention arm including taking her blood pressure and texting the result either once or twice daily for seven days after discharge from the hospital. She will be told a text message will be sent every morning saying "Good morning. Please send us a morning blood pressure reading." and that she will receive a text message back based on the value of her reading. Women will be informed that while the platform is HIPAA compliant, text messaging is not a completely secure means of communication.

Potential study risks:

There is a risk of loss of confidentiality in patients randomized to the intervention arm as texting technology was not built for secure communications. Therefore, privacy of information sent through text messaging cannot be completely guaranteed. However, as texting has the potential to be a more patient-centered, effective means of remote surveillance, we believe the potential benefits outweigh the risks. Additionally, patients will only be texting blood pressure readings and responses in the text messages have minimum information necessary to reduce the chance of someone else seeing any details about their health. The platform includes only the patient's name and cell phone number, each matched to a study ID number. The privacy policy of WaytoHealth ensures that no information shared with the site will be sold or distributed and the site is password protected. Patients will be encouraged to have a security lock on their phones. As only those with unlimited texting services will be included in the study, there is no additional financial cost to receiving or sending text messages.

Potential study benefits:

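### The consent discussion describes seven days of texting after discharge, while the study duration is 14 days: an internal inconsistency to correct, with no shown effect on the outcomes or sample size

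*Combined protocol and SAP*

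**What the plan says.** All places are in the combined protocol and SAP.

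- **Consent process, Overview.** What the woman is told about the intervention arm includes taking her blood pressure and "texting the result either once or twice daily for seven days after discharge from the hospital".
- **Study duration.** "The subjects will participate in the study for two weeks (14 days) following discharge if they are randomized to the text-message arm".
- **Procedures.** "Patients receive reminders to text message their blood pressures twice daily for two weeks postpartum, starting on the day after discharge". The same section places randomization after consent.
- **Design.** Remote surveillance by text lasts two weeks.
- **Abstract.** Women in the texting arm will "text in blood pressures for two weeks postpartum".
- **Background, on the earlier pilot of 32 women.** "They were asked to send in blood pressures on the seven days following discharge from the hospital after their delivery". This is the only other place where a seven-day texting schedule is described.

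Three further statements bear on the consequences. The plan defines its primary endpoint as "the percentage of patients in which a single blood pressure is obtained in the first 10 days following discharge". For women in the text arm alone, it also assesses "the percentage of patients in whom blood pressure values are obtained at 72 hours and 7-10 days postpartum". The sample size section (under Accrual) takes from the pilot that "approximately 80% of patients text at least one blood pressure in the 7 days post discharge".

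**The concern.** The consent Overview is current text that governs what staff say to women in this trial. It is neither a description of the pilot nor superseded wording. It does not say at least seven days or the first seven days; it gives seven days as what the arm requires. Every other statement about this trial's texting arm says two weeks or 14 days.

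How long she must keep texting is the main demand that the intervention makes on a newly delivered woman. Because consent precedes randomization, women who end up in either arm would hear the wrong figure. At stake is an accurate account of the burden at consent. Training staff on the protocol, as planned under Resources necessary for human research protections, does not cure this, because the number is wrong in the protocol itself.

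**Working it through.** **Durations counted from discharge.** The inputs are 7 days (consent Overview) and 14 days (Study duration). Both run from discharge, so the ratio does not depend on the day of discharge.

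- Ratio: 7 / 14 = 0.50, a shortfall of 50%.
- Readings requested at once daily: 7 × 1 = 7 against 14 × 1 = 14.
- Readings requested at twice daily: 7 × 2 = 14 against 14 × 2 = 28.

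**If two weeks postpartum (Abstract, Procedures) is counted from delivery.** Background equates postpartum days 4-6 with post-discharge days 3-5 after vaginal delivery and 2-4 after cesarean. If the day of discharge is day 0, discharge falls on postpartum day 1 or 2.

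- Vaginal: 14 − 1 = 13 days after discharge; 7 / 13 = 54%, so 46% short.
- Cesarean: 14 − 2 = 12 days after discharge; 7 / 12 = 58%, so 42% short.

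The document states no discharge day, so this depends on the counting convention. If the day of discharge is day 1, discharge falls on postpartum day 2 or 3, and the ratios are 7 / 12 = 58% and 7 / 11 = 64%. Seven days falls well short on any of these counts.

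**Sample size.** The plan's 103 per arm is reproduced by a two-sided comparison of 50% with 70% (the 1.4-fold increase: 0.50 × 1.4 = 0.70) at alpha 0.05 and 80% power.

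- Uncorrected: n = (1.960 × √(2 × 0.6 × 0.4) + 0.842 × √(0.25 + 0.21))² / 0.2² = 93.
- With continuity correction: n = (93/4) × (1 + √(1 + 4/(93 × 0.2)))² = 103.

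No texting duration enters this calculation, so correcting the consent text leaves 103 unchanged.

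**Primary outcome.** The window is post-discharge days 1-10. A seven-day schedule occupies days 1-7, which is 7 of the 10, and one reading is enough. The planning figure of about 80% was itself observed over 7 days.

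**Assessment at 72 hours and 7-10 days postpartum.** With discharge on postpartum day d, a seven-day schedule starting the next day runs from day d + 1 to day d + 7.

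| Discharge day d | Seven-day schedule (postpartum days) | Days of the 7-10 window covered |
|---|---|---|
| 1 | 2-8 | 2 of 4 |
| 2 | 3-9 | 3 of 4 |
| 3 | 4-10 | 4 of 4 |

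A 14-day schedule covers all four days in each row. The seven-day schedule still reaches at least two, and a woman who kept to it would have a value in the window. The 72-hour value depends on when texting starts, and the two durations do not differ in that.

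**The case against.** The best case on the other side is that this is one number in a narrative paragraph, probably carried over from the pilot. The operative sections agree on two weeks. The platform sends an introductory text on the day of discharge and reminders for the full period, staff are educated on the protocol, and women may stop at any time. Each woman also receives a consent form, which is not in the documents and may already be right. Those points limit the consequences and support a low severity. They do not correct the sentence: the texts and reminders come after consent, and a correct form would only mean that staff contradict it aloud. The carry-over is an inference, and it would explain the error without removing it.

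A reader might infer more, in four ways that the documents do not support.

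- **That the 7-10 day postpartum assessment is compromised.** The natural reading of that measure is one value in the window, not a value on each of four days. A seven-day schedule covers at least two of the days, so at most some women lose extra chances to supply a late reading.
- **That the shortfall is 50% on any reading.** That holds against Study duration. Against two weeks counted from delivery it is smaller.
- **That the plan contradicts itself on frequency or prompts.** In Procedures, twice daily could describe the reminders or the texting. The consent Overview quotes one morning message without saying that it is the only one. This needs confirming, but it is not a demonstrated conflict.
- **That women are misinformed in writing.** Without the consent form this cannot be known.

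**Conclusion.** The inconsistency is real, and the consent Overview is wrong as written. It describes seven days of texting where the plan sets 14 days following discharge: 50% of the duration in Study duration, or about 54-58% if two weeks postpartum runs from delivery and discharge is on about postpartum day 1 or 2. The second range rests on the discharge timing implied in Background with the discharge day counted as day 0.

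The consequence is an inaccurate account of the intervention's burden at consent. The documents show no effect on the primary outcome, the sample size of 103 per arm or the 7-10 day postpartum assessment. The two-week design itself is not in question. Severity is minor.

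**What to change.** 1. In the consent Overview, replace the seven-day period with two weeks (14 days) following discharge, starting the day after discharge.
2. Have the investigator confirm how often women are asked to text, and state that frequency in the same way in the consent Overview and in Procedures. At present one says once or twice daily and the other has twice-daily reminders.
3. Check that the consent form gives the same duration and frequency, and amend it only if it does not.

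The cost is an edit to one sentence, an aligned statement of frequency and a check of the form. No patients, visits or procedures are added.
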